9.1.1 Unanticipated Adverse Device Effects

UADEs will be summarized separately for all UADEs, UADEAEs by maximum intensity, UADEAEs by strongest relationship to study device. Each subject will be counted only once within each level of summary (system organ class and preferred term). If a subject experiences more than one AE in each level, the AE with the strongest relationship or the maximum severity, as appropriate, will be included in each summary for AE relationship and severity.

All UADES and UADEs leading to discontinuation of Enteral Feeding will be presented in a listing.

9.1.2 Serious adverse events

Serious Adverse Events (SAEs) will be listed separately but not summarized.

9.1.3 Deaths

All deaths that occur during the study will be presented in a subject listing.

9.2 Gastrointestinal (GI) Symptom Diary

The gastrointestinal symptoms recorded in the 7 day gastrointestinal symptom diary during the observation and run in periods will be compared with the symptoms recorded three separate times during the treatment period.

The following descriptive summaries will be provided for each period: Visit 1 (Days -14 to -8), Visit 2 (Days -7 to -1), and Visit 3 (Days 23 to 30), Visit 4 (Days 53 to 60), and Visit 5 (Days 83 to 90) under RELiZORB:

- Number of subjects who experienced a symptom at least once during the period (incidence) overall and for each symptom
- Number of days each symptom occurred within a period.

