### Safety

- Frequency and severity of adverse events and unanticipated adverse device effects (UADEs)
- Evaluation of clinical and laboratory findings
- · Concomitant medication assessment
- Frequency and severity of gastrointestinal signs and symptoms (abdominal pain, vomiting, loss of appetite, bloating, flatulence and steatorrhea)

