# 4.9.11 Gastrointestinal Symptom Diary

Detailed verbal instructions on how to record entries in the gastrointestinal symptom diary should be conducted by study staff on Day -14 and again as a subsequent reminder on Days 0, 30, and 60. The gastrointestinal symptom diary will also include a brief instruction. Entries need to occur on a daily basis for 7 consecutive days. The completed symptom diary will be entered into the eCRF and regarded as a source document. Diary data will be used for the primary safety study endpoint to determine the frequency and severity of gastrointestinal symptoms.

Title: Absorption and Safety with Sustained Use of Relizorb™ Evaluation (Assure) Study in Patients With Cystic Fibrosis Receiving Enteral Feeding

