## 7.7 Safety Analysis

Safety will be assessed based on the incidence, severity, and type of AE and UADE, clinically significant changes or abnormalities in the subject's clinical laboratory results and vital signs. For clinical laboratory tests, descriptive summaries of actual values and changes from the baseline will be presented. Descriptive statistics will be provided for vital sign measurements collected during clinic visits.

AE and UADEs will be recorded throughout the study and listed in summary tables in terms of severity and causal relationship to Relizorb use. Relationship assessments that indicate the AE is "Not Related" is an event related to etiology, rather than from Relizorb use. "Related" is defined as an association between the AE or UADE and Relizorb use. Other selections include "Possibly Related" and "Probably Related".

The gastrointestinal symptoms recorded in the 7 day gastrointestinal symptom diary during the run in period will be compared with the symptoms recorded three separate times during the treatment period. Each symptom will be categorized as a) occurring or not occurring b) rated as a 1,2, or 3 in severity, and lasting in duration for less than 15 minutes, 15 to 30 minutes, 31 to 60 minutes, or greater than 60 minutes.

For the comparison between symptoms recorded during the run in period and the treatment period, the following analyses will be performed:

Number of days where any symptom occurred;

Title: Absorption and Safety with Sustained Use of Relizorb™ Evaluation (Assure) Study in Patients With Cystic Fibrosis Receiving Enteral Feeding

- Number of days each symptom occurred;
- For each symptom, number of days when the severity was a 1, 2, and 3
- For each symptom, number of days when the symptoms lasted in duration for less than 15 minutes, 15 to 30 minutes, 31 to 60 minutes, or greater than 60 minutes.

Comparison of these values during the run in and treatment periods will be performed using analysis of variance (ANOVA).

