2.2 Safety, Efficacy and Exploratory Endpoints

2.2.1 Safety Endpoints

The safety and tolerability endpoints include the following:

- Frequency and severity of adverse events
- Incidence of gastrointestinal symptoms.
- Unanticipated adverse device effects (UADE)
- Evaluation of clinical and laboratory findings
- Vital signs
- · Concomitant medications

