6. GENERAL ISSUES FOR STATISTICAL ANALYSIS

6.1 General Statistical Methodology

The primary population for safety is the safety population. For the efficacy analysis, the primary endpoint will be conducted on both the per protocol (PP) and ITT populations. All secondary efficacy analyses will be conducted on the ITT population unless otherwise specified.

Continuous variables will be summarized using descriptive statistics, including number of nonmissing values, mean, standard deviation, median, minimum, and maximum. Qualitative variables will be summarized using the number and proportion of each possible value.

The minimum and maximum will be reported with the same degree of precision (i.e., the same number of decimal places with a maximum of 1 decimal place) as the raw data. Measures of location (mean and median) will be reported to 1 degree of precision (with a maximum of 2 decimal places) more than the raw data and the measure of spread (standard deviation) will be reported to 2 degrees of precision (with a maximum of 3 decimal places) more than the raw data. All efficacy endpoints in section 8.1 will use a maximum of two decimal places.

Categorical (qualitative) variable summaries will include the frequency and percentage of subjects who are in the particular category. The denominator for the percentage calculation will be based upon the total number of subjects in the relevant study population unless otherwise specified.

Assessments done on unscheduled visits will not be summarized but will be listed. If any assessments are repeated on the same day and/or time point, the last non-missing assessment will be summarized and/or analyzed.

Statistical tests will be conducted at the 0.05 significance level using 2-tailed tests, and nominal p-values will be reported. SAS software (SAS, Inc., Cary, NC) will be utilized for statistical analysis (version 9.3).

Subject level information presented in a listing will include subject identification number as well gender, age (examples: F/23, M/37). All listings will be sorted by subject identification numbers.

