10. CHANGES FROM PLANNED ANALYSIS

The following items were changed from the planned analysis specified in the protocol:

Protocol Version 2.0	Updated Planned Statistical Analysis Changes From the Protocol	Justification For Change
7.4.2 Safety Population The safety population includes all subjects who received at least one RELiZORB exposure. For subjects who withdraw from the study, every effort will be made to retrieve safety information.	7.4.2 Intent to Treat The ITT population, includes all subjects who received at least one RELiZORB exposure. This population is the same as safety and will be referenced as ITT for efficacy analysis.	To clarify study populations for safety and for efficacy analysis.
Section 7.5 Procedures for Handling Missing, Unused and Spurious Data All available safety and tolerability data will be presented in data listings and tabulations. No data imputation will be applied for missing values.	Section 6.2 Handling of Missing Data Available subject data will be used in the statistical analysis. For the MMRM analysis, subjects who lack all post-baseline measures, the baseline efficacy outcome will be imputed for all post-baseline responses (i.e., no change from baseline).	There really is no change for subjects who are missing post-baseline data.

Section 7.7 Safety Analysis (paragraph 3) For the comparison between GI symptoms recorded during the run in period and the treatment period, the following analyses will be performed: No. of days where any symptom occurred; No. of days each symptom occurred; No. of days when severity was 1, 2 or 3 Symptom duration of <15min, 15-30min, 31-60min or >60min.	Removal of GI symptoms analysis: No. of days when severity was 1, 2 or 3 Symptom duration Any GI comparisons using ANOVA	Based on the fact that the GI symptom diary is a self-reporting diary, where collection of input like severity of symptoms is not validated, analysis is descriptive.
Section 7.8 Efficacy Analysis Comparison of these values during the run in and treatment periods will be performed using analysis of variance (ANOVA).	Analysis updated to a repeated measures analysis to compare mean values at baseline to Days 30, 60, and 90.	The MMRM statistical model in the SAP is an extension of the proposed model and accommodates random and fixed effects in the context of repeated measures.

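### SAP 9.2 sets no denominator for GI diary incidence, so unless the table shell says otherwise the SAP 6.1 default treats an exposed subject with no diary as symptom-free

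*SAP*

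**What the plan says.** **Diary summaries.** SAP 9.2 sets the observation and run-in diaries against three on-treatment diaries. It plans two descriptive summaries per period: the "Number of subjects who experienced a symptom at least once during the period (incidence) overall and for each symptom", and the days on which each symptom occurred. It gives no denominator, no minimum number of diary days and no rule for a missing diary.

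**Default rule.** SAP 6.1 states: "Categorical (qualitative) variable summaries will include the frequency and percentage of subjects who are in the particular category". It continues: "The denominator for the percentage calculation will be based upon the total number of subjects in the relevant study population unless otherwise specified". SAP section 9 and the entry for Table 14.3.3.1 in SAP 12.1 make the relevant population the safety population. SAP section 5 defines that by a single use of the device; no diary is required.

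**Period labels.** SAP 9.2 labels the on-treatment periods Days 23 to 30, 53 to 60 and 83 to 90. Protocol 4.3 has a 7-day diary that ends the day before each visit.

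**Severity.** The protocol's GI safety endpoint (synopsis and 3.2) is "Frequency and severity of gastrointestinal signs and symptoms". Protocol 4.9.11 says: "Diary data will be used for the primary safety study endpoint to determine the frequency and severity of gastrointestinal symptoms". Protocol 7.7 planned this summary: "For each symptom, number of days when the severity was a 1, 2, and 3". SAP 2.2.1 has "Incidence of gastrointestinal symptoms" only. SAP section 10 records the change: "Removal of GI symptoms analysis: No. of days when severity was 1, 2 or 3". It also removes duration and the ANOVA, on the ground that the self-reported diary, severity included, is not validated.

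**The concern.** The diary is the only planned before-and-during comparison of GI tolerability, and PERT with feeds stops when treatment starts. Protocol 2.4 expects symptoms to fall with the device. Under the default denominator, a subject who used the device once and then withdrew contributes a run-in diary and no later one, but remains in every later denominator. Shown incidence then falls as subjects leave, even if symptoms among those still reporting do not change. That fall would look like the expected benefit.

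Some loss is foreseeable. The protocol enrols about 35 subjects to obtain 30 who reach Day 60, and protocol 4.5 replaces early withdrawals. A withdrawn subject who was exposed stays in the safety population beside the replacement. Because that population requires exposure, and exposure starts at Day 0, withdrawals within it come after the run-in diary period.

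Symptom days have a related gap. If they are summarised as a continuous variable, SAP 6.1 gives the number of non-missing values, but nothing shows how many of the seven days each subject recorded.

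**Working it through.** The plan states no diary incidence or return rate, so it has no figure to reproduce. The check follows the SAP rule and shows its effect over a range.

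**Inputs**
- N, the safety population: 35 (Protocol 4.1), or 40 as the upper planned enrolment (Protocol 1.0, SAP 3.3). Assumption: every enrolled subject used the device at least once.
- d, subjects with a diary in the period: 30, the protocol's target for reaching Day 60, or 34 as a mild case. Assumption.
- x, subjects with the symptom in that diary. Assumption.

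**Formulas**
- Incidence among subjects with a diary: p = x/d.
- Incidence shown under SAP 6.1: s = x/N = p × d/N.

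**Attenuation factor d/N**
- 34/35 = 0.971
- 30/35 = 0.857
- 30/40 = 0.750. This pairs the highest enrolment with the minimum target, so it is an extreme case.

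**N = 35, d = 30**

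| x | p = x/30 | s = x/35 | Understated by (points) |
|---|---|---|---|
| 9 | 30.0% | 25.7% | 4.3 |
| 15 | 50.0% | 42.9% | 7.1 |
| 18 | 60.0% | 51.4% | 8.6 |
| 21 | 70.0% | 60.0% | 10.0 |

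**Effect on the comparison.** Suppose all 35 returned a run-in diary and 21 had the symptom: 21/35 = 60%.
- No change at Visit 4 (18/30 = 60%) is shown as 18/35 = 51.4%, an apparent fall of 8.6 points.
- A rise to 21/30 = 70% is shown as 21/35 = 60%, no change.
- The relative rise that is hidden is N/d − 1: 35/34 − 1 = 2.9%; 35/30 − 1 = 16.7%; 40/30 − 1 = 33.3%.

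**The direction can reverse.** If five diaries were missing at run-in and none at Visit 4, a constant 60% would be shown as 18/35 = 51.4% and then 21/35 = 60%, against the device.

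**Period lengths (last day − first day + 1).** Days −14 to −8: 7. Days −7 to −1: 7. Days 23 to 30, 53 to 60 and 83 to 90: 8 each. A diary ending the day before a visit on its nominal day gives Days 23 to 29, 53 to 59 and 83 to 89: 7 each.

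**The case against.** **The shells may settle it.** The SAP contents list table shells that are not in the text available for review, and SAP 6.1 allows another denominator to be specified. A shell for Table 14.3.3.1 could do so. This stands, and it makes the point conditional.

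**Other text points the other way.** SAP 6.2 uses available data, and protocol 7.5 rules out imputation for missing values. Counting an absent diary as no symptoms sits badly with both. But neither sets a denominator, while SAP 6.1 does. SAP 9.2 itself asks only for a number of subjects; a raw count also falls as diaries are lost.

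**The count could be recovered.** Discontinuations are tabulated and diaries are listed (Listing 16.2.7.1), and no test or decision depends on the table. This limits the harm, but the printed percentage would still mislead.

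**Bias in favour of the device.** A reader might infer that the error must flatter Relizorb. The documents do not support that. It requires more missing diaries on treatment than before it. That is plausible, but no return rate is given.

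**Severity.** A reader might infer that severity was dropped without notice, or that worsening would go unseen. Neither follows. SAP section 10 discloses the removal, and its reason names severity itself. Protocol 6.2 counts a pre-existing condition that worsens after device use as an adverse event, and SAP 9.1 includes maximum severity in its overview of adverse events. What remains is narrower: section 10 does not list the change of endpoint, no diary table shows severity, and the only planned table of severity by preferred term is for UADEs.

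**Conclusion.** The denominator point holds on the SAP text as supplied, with medium confidence. SAP 6.1 states a default, SAP 9.2 does not override it, and the result is that an exposed subject without a diary is treated as symptom-free. The illustrated understatement is a factor of 0.971 with one diary missing of 35 and 0.857 with five missing of 35, or 10 points when 21 of 30 have the symptom. These sizes rest on assumed diary numbers, full exposure of enrolled subjects and a silent shell. The before-and-during comparison is distorted only if diary loss differs between the periods, and in the device's favour only if it is greater on treatment.

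The 8-day labels are minor and probably a labelling slip. They change results only if used as date filters. The severity change is a disclosed choice with a stated reason; a descriptive table would be a reasonable addition, and its absence does not show an error.

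**What to change.** In SAP 9.2:
1. Use subjects with a diary for the period as the incidence denominator, and print the numbers of safety subjects with and without one.
2. Report days recorded beside symptom days.
3. Assign entries to a period by the diary they belong to (observation, run-in, Visit 3, 4 or 5). Visits may move by 4 days, so nominal days are unreliable. Correct the on-treatment labels to 7 days.
4. Make the shell for Table 14.3.3.1 agree.

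Optional: list in SAP section 10 the change of endpoint from frequency and severity to incidence. Consider one untested descriptive table of the severity ratings by symptom and period, with a note that the scale is not validated.

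**Cost.** SAP wording and at most one more table. Protocol 7.7 already has symptoms rated 1 to 3, so no new data are needed. **Downside.** Percentages among subjects with a diary can still look better if those with worse symptoms leave, which is why the number without a diary must be shown. The optional table adds more unvalidated self-report.

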14.2.1.7	ITT	Changes over Time in Serum Protein Concentrations (Total Protein, Prealbumin, Albumin, and Transferrin)	16.2.5.6.1
14.2.1.8	ITT	Changes over Time in Urinary Leukotriene E4	16.2.5.7.1
14.2.1.9a	ITT	Changes over Time in Plasma Concentrations of Fat Soluble Vitamins (A, D, and E)	16.2.5.5.1
14.2.1.9b	ITT	Changes over Time in Plasma Concentrations of Fat Soluble Vitamins (A, D, and E) by Age Subgroup	16.2.5.5.1
14.2.1.10	ITT	Weight and Body Mass Index (BMI) Z-scores by Age Subgroup and Comparison to Historic Z-score	16.2.5.10.1
14.2.1.11	ITT	Changes over Time in Weight Gain Velocity (g/kg/90 days) Compared to Historical by Age Subgroup	16.2.5.9.1
14.3.1.1	Safety	Summary of Adverse Events	16.2.6.1, 16.2.6.2, 16.2.6.3, 16.2.6.5
14.3.1.2	Safety	Adverse Events by System Organ Class and Preferred Term	16.2.6.1
14.3.2.1	Safety	Unanticipated Adverse Device Effects by System Organ Class and Preferred Term	16.2.6.3
14.3.2.2	Safety	Unanticipated Adverse Device Effects by System Organ Class, Preferred Term, and Relationship	16.2.6.3
14.3.2.3	Safety	Unanticipated Adverse Device Effects by System Organ Class, Preferred Term, and Severity	16.2.6.3

Table Number	Population	Title	Listing Reference
14.3.3.1	Safety	Gastrointestinal Symptom Diary: Frequency and Incidence – Overall and by Symptom	16.2.7.1
14.3.4.1	Safety	Summary of Clinical Chemistry Measurements: Results and Change from Baseline	16.2.8.1
14.3.4.2	Safety	Summary of Hematology Measurements: Results and Change from Baseline	16.2.8.2
14.3.4.3	Safety	Summary of Numeric Urinalysis Measurements: Results and Change from Baseline	16.2.8.3
14.3.4.4	Safety	Summary of Blood Lipids: Results and Change from Baseline	16.2.8.4
14.3.5.1	Safety	Summary of Vital Sign Measurements: Results and Change from Baseline	16.2.9.1
14.3.6.1	Safety	Concomitant Medications	16.2.3.3

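### SAP 9.2 omits the protocol's count of days with any GI symptom without declaring it, so the only overall measure it defines is yes/no per diary period

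*SAP*

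**What the plan says.** Protocol 4.9.11 gives the diary a leading role: "Diary data will be used for the primary safety study endpoint to determine the frequency and severity of gastrointestinal symptoms". The symptoms named in the protocol's safety endpoints are "abdominal pain, vomiting, loss of appetite, bloating, flatulence and steatorrhea", and the diary is filled in daily for seven consecutive days.

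Protocol 7.7 opens its list of diary analyses with "Number of days where any symptom occurred". It then adds days per symptom, days by severity grade and days by duration, with run-in and treatment compared by ANOVA.

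SAP 9.2 makes the diary analysis descriptive and defines two summaries per diary period. One is "Number of subjects who experienced a symptom at least once during the period (incidence) overall and for each symptom". The other is "Number of days each symptom occurred within a period".

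SAP section 10 repeats the protocol item, "No. of days where any symptom occurred", in its protocol column. Its change column begins "Removal of GI symptoms analysis: No. of days when severity was 1, 2 or 3" and goes on to symptom duration and the ANOVA comparisons. Days with any symptom is not among the removed items.

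Table 14.3.3.1 in SAP 12.1 is titled "Gastrointestinal Symptom Diary: Frequency and Incidence – Overall and by Symptom".

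**The concern.** Once severity and duration are gone, days with any symptom would be the one remaining measure of overall symptom burden. SAP 9.2 leaves it out, and the overall row that remains records only whether a subject had any symptom at all during the period. A subject who goes from six symptom days to two is a yes both times.

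This matters because the protocol expects fewer malabsorption symptoms with the device, while treatment also changes the formula and ends PERT with feeds. Overall improvement or worsening is what a reader will look for first. A programmer who follows 9.2 literally would not produce the count that answers this.

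Section 10 does not explain the gap. Its reason is that inputs such as severity in a self-reported diary are not validated. That cannot be a reason to leave out days with any symptom when days per symptom, taken from the same entries, are kept.

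**Working it through.** **The text.** The plan gives no power or precision figure for the diary. Its only power statement, 80% with 30 subjects at effect size 0.53, concerns DHA; a paired two-sided t-test reproduces it at 80.1%. For the diary, the check starts with the four places side by side.

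| Place | Days with any symptom |
|---|---|
| Protocol 7.7 | planned |
| SAP 9.2 | not listed |
| SAP 10, removed items | not listed as removed |
| Table 14.3.3.1 title | can be read as including it |

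**Can it be rebuilt from what remains?** Not from the summaries. Take two subjects who each have six symptoms on one day apiece. In the first, all six fall on the same day, giving 1 day with any symptom. In the second, each falls on a different day, giving 6. Their per-symptom day counts and their at-least-once results are identical. The count can be derived only from the daily records.

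**How much can the yes/no row miss?** The documents give no symptom rate, so every rate below is an assumption.

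*Identical subjects, independent symptoms and days.* Suppose six symptoms each occur on 10% of days, and this falls by 30% to 7%.
- Days with any symptom: 1 − 0.9^6 = 46.9% falls to 1 − 0.93^6 = 35.3%, or 3.28 to 2.47 days per week.
- At least once, overall: 1 − 0.9^42 = 98.8% falls to 1 − 0.93^42 = 95.3%.
- At least once, one symptom: 1 − 0.9^7 = 52.2% falls to 1 − 0.93^7 = 39.8%.

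*Subjects differ, and each changes by the same proportion.* Let the daily probability p of any symptom follow a beta(a, b) distribution across subjects with dispersion ρ = 1/(a + b + 1). Incidence is 1 − E[(1 − fp)^7], where f multiplies each subject's p. At a mean of 50% and ρ = 0.1, a = b = 4.5. Before the change, E[(1 − p)^7] = (4.5/9)(5.5/10)…(10.5/15) = 0.0315, so incidence is 97%. With f = 0.7 it is 92%.

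| Mean % of days | ρ | Relative fall | Mean days per week | At-least-once incidence |
|---|---|---|---|---|
| 50 | 0.1 | 30% | 3.5 to 2.45 | 97% to 92% |
| 50 | 0.3 | 30% | 3.5 to 2.45 | 89% to 84% |
| 30 | 0.6 | 50% | 2.1 to 1.05 | 52% to 43% |
| 20 | 0.3 | 50% | 1.4 to 0.7 | 54% to 40% |
| 10 | 0.1 | 50% | 0.7 to 0.35 | 43% to 27% |

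*Mean halved with ρ held fixed.* Here some subjects become nearly symptom-free, and the yes/no row responds more. At ρ = 0.4, a fall from 4.2 to 2.1 days moves incidence from 90.4% to 63.8%, and a fall from 1.4 to 0.7 days moves it from 48.0% to 27.1%.

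**Information lost.** The SAP plans no diary test, so power serves here only as a yardstick. The simulation used 30 pairs, the proportional-change model with ρ = 0.1 and 0.3, a 30% fall, an exact McNemar test on yes/no and a paired t-test on days.

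| Mean % of days | Day count | Yes/no |
|---|---|---|
| 50 | 87% to 90% | 1% to 2% |
| 30 | 55% to 61% | 6% to 8% |
| 20 | about 37% to 40% | about 6% to 10% |
| 10 | about 19% | about 3% to 7% |

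**The case against.** The strongest reply is that the count may never have been dropped. Section 10 names it and does not remove it. Incidence is defined in 9.2 as at least once, so the separate word frequency, paired with overall in the table title, reads naturally as an overall day count. The table shell would settle the matter, but it is not in the text available for review and its absence cannot be held against the plan. This stands: the documents show an inconsistency and do not show a decision to delete.

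A reader might also infer that GI tolerability as a whole has been cut down to a yes/no measure. It has not. Days and incidence for each symptom remain for all five diary periods, and the diary is listed by subject. In the 10% illustration, single-symptom incidence is mid-range and moves visibly. A large change in one symptom would still show.

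A third inference is that nearly every subject will report something each week, so the overall row sits at its ceiling. No rate in the documents supports this. Over the assumptions tried, weekly incidence ran from about 15% (10% of days, ρ = 0.8) to 100%. If the effect were complete resolution in some subjects, the yes/no row would serve well.

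Finally, the power figures describe tests that nobody plans, and at low symptom rates the day count is weak too. That is fair, and they are used here only to compare two summaries of the same data.

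**Conclusion.** The point holds in a limited form. SAP 9.2 omits a summary that protocol 7.7 plans. Section 10 neither declares nor justifies the omission, and the table title points the other way. As written, the only across-symptom measure 9.2 defines is yes/no over the period, and the per-symptom summaries cannot replace the missing count.

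The size of the loss depends on symptom rates that the documents do not give. If subjects change by a common proportion, the yes/no row can move by about five percentage points while mean symptom days fall by 30%, and the day count was the more informative summary at every assumed rate shown. If some subjects become symptom-free, the loss is smaller. The documents do not establish that the overall row will be at a ceiling, or that a change in symptoms would go unseen in the planned output as a whole.

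**What to change.** Add the number of days with any symptom, for each diary period, to SAP 9.2 and to Table 14.3.3.1. Summarise it descriptively, with the within-subject change from the pre-treatment diary. State which pre-treatment diary is meant: protocol 7.7 uses the run-in, while SAP 9.2 shows both observation and run-in. A 95% confidence interval for the change would help but is optional, since the protocol does not ask for one. Keep the at-least-once row.

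Align section 10 so that its list of removed items matches 9.2. If the sponsor does mean to drop the count, section 10 should say so and give a reason that applies to it.

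When the bullet is written, fix the number of diary days counted. The on-treatment windows in 9.2 span eight days if read inclusively (30 − 23 + 1 = 8), against seven for each pre-treatment period. A day count needs the same base throughout.

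The cost is one SAP bullet and a few table rows from diary data already collected, with no added burden on subjects.
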